## **6. Study process**

### **6.1. Summary of Study Process**

- If the patient meets the inclusion criteria, the patient is invited to participate in the study and then the informed consent procedure for the clinical trial is applied.
- Assess patients' eligibility based on the inclusion/exclusion criteria.
- If the patient meets the inclusion/exclusion criteria, information prior to ERCP will be collected
- If the patient is enrolled, he will be randomized
- ERCP is performed after informed consent. Any intraoperative adverse events are recorded on the CRF for submission and subsequent analysis.
- Follow-up will be performed from the postoperative to the study completion, as detailed in the time and event table.

### **6.2. Enrollment**

Only after patients signed the informed consent, can the research-related procedures be conducted.

### 6.2.1. Informed Consent

According to the Helsinki Declaration, patients are not allowed to participate in the study without adequate informed consent. The principal investigator is responsible for ensuring that no patient was enrolled in the study without adequate informed consent. Failure to obtain informed consent and failure to document this process is considered a violation of the Helsinki Declaration and the study protocol.

All informed consent documents (ICDs) must be approved by ethics. Patient's informed consent requires documentary record on the informed consent by himself in his primary language.

The investigator or trained designated person performs a preliminary screening to determine if the patient generally meets the eligibility criteria for the study. If yes, the investigator or trained designee should recommend the patient to participate in the study. If the patient agrees to participate, they will need to sign an informed consent document.

The investigator or trained designated person should confirm that the subject understands the following points in the study:

- The purpose of research,
- Potential risks or adverse events,
- Potential risks or adverse events directly related to participating the research,
- The likelihood of failure,
- Research requirements include follow-up visits,
- All rights of the subject as a participant in the clinical study.

After explaining the purpose of the study, the investigator or trained designee should answer any questions from the subject. If the subject agrees to participate, his or her wishes must be recorded by signing and dated on the EC-approved ICF, and the document should be signed and dated by the patient receiving the informed consent.

After successful completion of the informed consent process, the investigator or trained designated person will assess the eligibility of patients based on the protocol.

### 6.2.2. Patient Selection

All patients who underwent ERCP, agreed to use EndoAngel and generally meet the study requirements were screened based on the inclusion/exclusion criteria. Patients who passed the screening were enrolled and recorded in the subject screening and enrollment tables. There is no bias in the choice of the enrolled subjects. The date of screening, the results (enrolled or not), and the primary reason for not selecting subjects (such as not meeting inclusion criteria, or not interested in participating in the study) will be recorded.

After the patients are enrolled, the research center should complete the preoperative study data collection.

It is desirable to be able to collect complete data for all enrolled patients, without who withdrawal from the study.

### **6.2.3 Subject identification number**

Patients were numbered after signing informed consent.

The subject number begins with EA as a fixed number and is numbered starting from 0001 at the time of signing the informed consent. For example, the first patient who signed the informed consent was EA0001, and the second one was EA0002.

Once the subject identification number is assigned, the number is not reusable.

## **6.3 Treatment Description**

This section applies to individuals who have signed an approved informed consent and have been identified as eligible to participate in this study on the basis of the inclusion and exclusion criteria. This section introduces the preoperative, surgical and postoperative management of subjects in detail.

### **6.3.1 Patient Screening Assessments**

- 1) History
- 2) Physical examination
- 3) Hematuria pregnancy test (if required)

### **6.3.2 Pre-Procedure Managements**

- 1) Fasting for 6 hours and water deprivation for 2 hours before examination
- 2) Routine stomach preparation.
- 3) Psychological counseling.
- 4) Performing routine anesthesia for painless gastroscopy patients.

### **6.3.3 Intraoperative Managements**

- 1) Patient position: prone position with appropriate restraint.
- 2) Insertion route: according to the actual situation of the subject, usually through the esophagus
- 3) Routine observation

### **6.3.4 Post-operative Managements**

- 1) Postoperative routine nursing
- 2) The anesthetized subjects were observed until they woke up, and the ordinary subjects were observed until they left the endoscopic room.
- 3) Record complications (if any).

### **6.4 Suspension and withdrawal**

Patients who were screened and confirmed to be eligible for the study, signed the informed consent and completed the randomization were considered as enrolled. If serious program deviation, withdrawal, or death occurs, the subject study is considered to be suspended. If the subject discontinues the study after obtaining informed consent, the data before the discontinuation will still be included in the study-related analysis.

#### **6.4.1 Pre-Procedure**

In any time during the study period, even before ERCP, participants could withdraw their informed consent whenever necessary. Researchers can withdraw participants before surgery according to safety considerations in the inclusion and exclusion criteria.

#### **6.4.2 Intraprocedure**

For safety reasons, the investigator may have the subject quit during the procedure. For example, the patient is not suitable for receiving the instrument for the study or the endoscopists do not use the specified instrument for any reason. If the following serious cases occur, please withdraw during the operation:

- 1) Perforation
- 2) Bleeding
- 3) Allergy to narcotic drugs
- 4) Unable to complete ERCP due to obstruction or other reasons

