### 1.1. Time and Event Tables

Events	Screening period (d -30~-1)	The day of ERCP(d 0)	Follow up (d 1-14)
Informed Consent	X		
Basic characteristics	X		
Medical history/surgical history	X		
Inclusion/Exclusion Criteria	X		
Random		X	
ERCP		X	
Concomitant treatment	X	X	
Concomitant medication	X	X	
Adverse Events		X	X
Research completed			X

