### **4.2. Secondary Endpoints**

- 1) Intersection over union of bile duct segmentation: It was the ratio of union and intersection of bile ducts predicted by artificial intelligence devices and actual bile ducts
- 2) Intersection over union of bile duct matching model: It was the ratio of union and intersection between the bile ducts generated by the AI device and the actual bile ducts in ERCP
- 3) Success rate of stent placement: It was calculated by dividing total number of patients with stent placement by the number of successful patients.
- 4) Rate of adverse events: It was calculated by dividing the total number of patients undergoing stent placement by the number of patients who experienced adverse events.
- 5) Fluoroscopy time: It was the sum of the total X ray fluoroscopy time during the whole procedure.
- 6) Total amount of contrast medium: It was the total amount of contrast medium during the whole procedure.

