### **8.3. Hypothetical test**

The main assumptions are:

1. The use of EndoAngel can reduce the operation time of ERCP;
2. The use of EndoAngel can improve the success rate of stent placement;
3. The use of EndoAngel can reduce the rate of adverse events;
4. The use of EndoAngel can reduce the fluoroscopy time;
5. The use of EndoAngel can reduce the total amount of contrast medium.

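### The Section 6.4.2 withdrawal rule is triggered by trial outcomes, and it can take those patients out of the denominators of two secondary rates and out of adverse-event follow-up

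*Protocol*

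**What the plan says.** Section 6.4.2 lists four intraprocedural events: perforation, bleeding, allergy to narcotic drugs, and "Unable to complete ERCP due to obstruction or other reasons". For these it instructs: "If the following serious cases occur, please withdraw during the operation". The rule stands within Section 6.4, on suspension and withdrawal, which states: "If serious program deviation, withdrawal, or death occurs, the subject study is considered to be suspended". The same section adds that, for a subject who discontinues after consent, "the data before the discontinuation will still be included in the study-related analysis". Section 6.4.3 speaks of subjects discontinued before or during ERCP and says that they are not replaced.

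Section 4.2 defines the adverse-event rate as "dividing the total number of patients undergoing stent placement by the number of patients who experienced adverse events". Stent success is defined in the same way, on patients with stent placement. Both ratios are written upside down; I take the stent-placement patients to be the intended denominator.

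On recording, Section 6.1 says: "Any intraoperative adverse events are recorded on the CRF for submission and subsequent analysis". Section 1.1 schedules adverse-event collection on the day of ERCP and on days 1 to 14, whereas the Section 1 summary gives one week of follow-up. Section 8.3 attaches a directional hypothesis to each rate: better stent success (hypothesis 2) and, for safety, "The use of EndoAngel can reduce the rate of adverse events" (hypothesis 3).

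**The concern.** The withdrawal triggers occur after randomisation and are outcomes. Perforation and bleeding are adverse events, and an ERCP that cannot be completed is the plainest form of unsuccessful stent placement. Whether a patient meets a trigger may depend on the arm, since the device is meant to guide the wire and the stent position.

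Two things are at stake. First, if having a stent placed is a condition for entering the denominator, the two arms are compared on subsets selected after randomisation, and the patients left out include those with the worst result. Second, if withdrawal ends the subject's participation, the scheduled adverse-event visits have no stated basis for the patients in whom they matter most. An analysis plan could redefine a denominator, but it could not recover follow-up that was never collected.

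**Working it through.** **Inputs.** Total enrolment is 62 (Section 8.4) with 1:1 allocation (Section 6.5.1), so 62/2 = 31 per arm. The protocol gives no adverse-event rate, no stent-success rate and no rate of incomplete ERCP. All event counts below are assumptions that show direction only.

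**The plan's own figure.** The 62 rests on procedure time and does not bear on these rates. It reproduces: difference 43.9 − 35 = 8.9 minutes, SD 11.56, two-sided 5%, power 80%, t-test gives 28 per arm, 56 in total; 56/0.9 = 62.2 and 56 × 1.1 = 61.6.

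**Stent success.** Let n patients start ERCP and f of them have a procedure that cannot be completed, with no other cause of failure.
- All who start as the base: (n − f)/n.
- Section 4.2 read literally, only patients with a stent as the base: (n − f)/(n − f) = 100%, whatever f is.
- Assume 20% incomplete in control and 10% in the experimental arm. Control: 31 × 0.20 = 6.2 leave, 24.8 remain; true success 24.8/31 = 80%, reported 100%. Experimental: 31 × 0.10 = 3.1 leave, 27.9 remain; true success 27.9/31 = 90%, reported 100%.
- A true difference of 10 points is reported as 0. The direction for each arm is clear: removing failures can only raise the success rate.

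**Adverse-event rate.** Assume a = 6 patients with an event among n = 31, and w = 2 or 3 patients withdrawn before stenting, all of whom had an event.

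| Reading | Formula | w = 2 | w = 3 |
|---|---|---|---|
| All who start ERCP as the base | a/n | 6/31 = 19.4% | 6/31 = 19.4% |
| Events kept, base restricted to stented patients | a/(n − w) | 6/29 = 20.7% | 6/28 = 21.4% |
| Withdrawn patients left out entirely | (a − w)/(n − w) | 4/29 = 13.8% | 3/28 = 10.7% |

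The second row is closest to the text: Section 4.2 restricts only the base, and Sections 6.1 and 6.4 keep the intraoperative event. It moves the rate up by about 1 to 2 points. The third row moves it down by about 6 to 9 points, but it uses a numerator rule that the protocol does not state. If the withdrawn patients had no event (an incomplete ERCP without complication), the base still shrinks and the rate again rises to 6/29 or 6/28.

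**Follow-up.** The rate counts patients, so a patient whose perforation or bleeding is on the CRF is already in the numerator. For that patient, what may be lost is the course of the event; Section 4.3 asks for its ending time and treatment result. A patient withdrawn for an incomplete ERCP without an event is different: a first event in the following days would be missed if participation has ended, which lowers the rate. This pulls against the denominator effect, so the net direction is not fixed.

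**The case against.** The strongest reply is that the protocol already protects these data. An event that triggers withdrawal has happened before the withdrawal; Section 6.1 sends it to the CRF for analysis, Section 6.4 keeps data up to discontinuation, and the full analysis set in Section 8.5 includes shedding cases. Section 6.4 does not say that only earlier data are kept, and no sentence ends adverse-event follow-up. Section 1.1 makes no exception for withdrawn patients. In this text, withdrawing during the operation might mean no more than stopping the procedure or the device. Since every trial patient needs drainage (Section 3.1), patients with stent placement could mean patients in whom placement was attempted, and a failed ERCP would then count as a failure.

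Much of this stands. A reader might infer that the rule erases perforations and bleeds from the trial, or that adverse-event rates are necessarily understated. Sections 6.1 and 6.4 contradict the first, and the second row of the table contradicts the second. A reader might also infer that the per-protocol main analysis drops these patients. Section 8.5 names that set in the context of the primary efficacy endpoints and does not call withdrawal a significant deviation, so the point does not rest on it.

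Two things remain. Recording an event does not put a patient without a stent into the Section 4.2 base. And the rule's place under suspension and withdrawal, with the wording of Sections 6.4 and 6.4.3, favours study withdrawal over merely stopping the procedure. The milder readings are possible, but the protocol does not choose them.

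**Conclusion.** The point holds as a conflict between stated rules. Section 6.4.2, read with Sections 4.2 and 6.4, allows patients with outcome events to leave both denominators and scheduled follow-up, against Section 1.1.

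- **Stent success:** on the literal base the rate is overstated in each arm, and a difference relevant to hypothesis 2 may be hidden. This assumes that the base is patients who received a stent; on an attempted-placement base the effect shrinks.
- **Adverse-event rate:** the denominator is formed after randomisation and follow-up may be incomplete, so the rate may be biased in either direction for hypothesis 3.
- **Size:** none can be stated. The percentages above depend on assumed counts; they show only that two or three patients move a rate visibly at 31 per arm.

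The endpoints are secondary, but one is the safety comparison and both carry directional hypotheses. The correction should be made.

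**What to change.** Reconcile Section 6.4.2 with Sections 1.1, 4.2, 6.1 and 6.4:

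1. State that ending the procedure, or the use of the device, is not withdrawal from the study.
2. State that adverse-event follow-up continues as scheduled unless the patient withdraws consent. Reconcile its length, which is one week in the Section 1 summary and days 1 to 14 in Section 1.1.
3. In Section 4.2, use all randomised patients who start ERCP, in the arm assigned, as the denominator for both rates, with the event count on top.
4. Count a procedure that is not completed as not successful for stent placement.

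The clinical decision to stop a procedure is left as it is. The cost is a few sentences of protocol text and, for a few patients, follow-up that is already scheduled. Reported stent success may look slightly less favourable.

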#### **6.4.3 Replacement**

Subject will be deemed to have commenced the study upon completion of the informed consent process, and any subject who has been discontinued prior to or during the ERCP will not subsequently be replaced by other subjects.

## 6.5 Randomization and Blinding

### 6.5.1 Randomization Implementation

Randomization is conducted according to the study protocol, and the random contents are implemented in an electronic system block-randomized manner (n = 4; experimental group/control group = 1). Randomization prior to ERCP to decide whether to use EndoAngel. The researchers randomized the random results generated by the electronic system, and the generated random results were stored in the research center. The random time (accurate to minute), random person, subject number and acronym were recorded in the corresponding positions of the electronic system.

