### 1.2. Flow chat

## 2. Introduction

Biliary stricture can be divided into benign biliary stricture and malignant biliary stricture, and malignant hilar biliary obstruction is the one of the common cause. Since there is no specific early screening method for malignant hilar biliary obstruction at present and most patients have no obvious clinical symptoms in the early stage, most patients are already in the advanced stage when they are first diagnosed. Advanced malignant hilar biliary obstruction cannot undergo resection surgery, whose first choice for the treatment is palliative endoscopic biliary drainage. Biliary drainage can relieve jaundice, pruritus and other symptoms due to cholestasis. However, before the narrow segment was placed the stent, the contrast agent could not pass through the narrow segment and the bile duct above the narrow segment could not be seen. So it was difficult for doctors to determine the direction of the guide wire and the position of the stent. In addition, indiscriminate application of the contrast agent may cause outflow obstruction leading to infection. However, there is no relevant research to solve these problems.

MRCP is the preferred examination method of pancreatic and bile duct diseases. Therefore, MRCP should be routinely performed before patients are treated with ERCP. At present, MRCP is in supine position, and ERCP is in prone position. Different positions lead to differences in the morphology of MRCP and the bile duct on ERCP. So preoperative MRCP in supine position has limited role in advising physicians on the morphology of the bile duct. Therefore, MRCP in the prone position is more favorable for endoscopists to perform ERCP.

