#### 3. Clinical trials

In addition to the criteria mentioned in the bile duct segmentation model, the clinical trials should also meet the following criteria:

- 1) Able to complete MRCP in prone position;
- 2) Patients requiring biliary drainage by ERCP due to malignant hilar biliary obstruction.

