### **3.3. Definition of enrollment**

After participants signed informed consent, they were randomized before ERCP. The randomization time was the enrollment time, and was recorded in CRF.

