## **4. Endpoints**

### **4.1. Primary Endpoint**

- 1) Procedure time: It was the time of performing ERCP.

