## 8.4. Sample Size Calculation

We mainly studied the effect of EndoAngel on the quality of ERCP for physicians. Therefore, data collection and analysis were conducted for the main effect. It is expected that a total of 62 subjects will be enrolled. Assuming the operation time of ERCP in experimental group is  $43.9 \pm 11.56$  minutes, the operation time of ERCP in control group is 35 minutes. Bilateral significance level 5% ( $\alpha = 5\%$ ), assurance 80% ( $\beta = 20\%$ ), shedding rate 10%, Expected to enroll 62 patients in total.

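### Randomisation (Protocol 6.5.1) does not fix the operator before the arm is revealed or record stricture class, which leaves a route to operator bias and forgoes precision on procedure time

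*Protocol*

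**What the plan says.** Protocol 6.5.1 sets the allocation scheme: "the random contents are implemented in an electronic system block-randomized manner (n = 4; experimental group/control group = 1". No stratification or minimisation factor is named there or elsewhere. The same section lists what the system records at randomisation: the time, the person randomising, the subject number and the acronym. Operator and stricture class are not among them.

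On timing, Protocol 3.3 says of participants that "they were randomized before ERCP", and the table in 1.1 puts randomisation and ERCP on the same day. The Summary has the operating physician work with or without the AI prompt, and 6.5.2 blinds only subjects and evaluators, so the operator knows the arm.

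The endpoint in 4.1 is "Procedure time: It was the time of performing ERCP". Section 8.4 gives the aim as "We mainly studied the effect of EndoAngel on the quality of ERCP for physicians".

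Eligibility for the randomised part (3.1) covers "Patients requiring biliary drainage by ERCP due to malignant hilar biliary obstruction", and the patient must be "Able to complete MRCP in prone position". The exclusions in 3.2 remove previous gastrectomy, stent replacement and pyloric or duodenal obstruction, but set no limit on the complexity of the stricture. The Introduction says that "MRCP should be routinely performed before patients are treated with ERCP".

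The number of operators is not stated. The Summary uses the singular. Section 6.4.2 uses the plural ("the endoscopists do not use the specified instrument for any reason"), which may be generic.

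**The concern.** How long a manual procedure takes plausibly depends on who does it and on the anatomy. The Introduction itself says that the stricture makes guide-wire direction and stent position hard to determine.

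Two separate things are at stake. First, nothing prevents the operator from being assigned after the arm is known. If assignment then depended on the arm, the arm effect would be mixed with the operator effect. That would be a bias, and a covariate in the analysis would not reliably remove it, least of all if operators and arms hardly overlapped. Second, even with the operator fixed beforehand, variance due to operator and stricture stays in the comparison unless both are recorded and used. Both can be known before randomisation, and the MRCP is already needed for the trial.

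**Working it through.** **Inputs from the protocol (8.4).** Means of 43.9 and 35 min, a difference of 8.9 min; SD 11.56 min; two-sided alpha 5%; power 80%; dropout 10%; total 62. Which arm carries the longer time is a separate question and does not affect the size.

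**Reproducing the size.** The normal approximation gives n = 2 × (1.96 + 0.8416)² × 11.56² / 8.9² = 26.5, so 27 per arm. The t-test version needs 28 per arm (power 80.8%), 56 in total, and 56 × 1.10 = 61.6, so 62. The plan's figure reproduces, with 11.56 used as the total SD.

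**Chance imbalance.** Assume a binary factor, such as one of two equally used operators. With 31 per arm, the SD of the difference in its share between arms is √(0.25 × 2/31) = 12.7 points. Simulating 20,000 lists of 62 in blocks of 4 gave 12.6 points, and a gap above 20 points in 9.6% of trials. If exactly half of the 62 patients have the factor, the exact hypergeometric chance of a gap of at least 20 points is 12.7%.

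**Shift from a given gap** = gap × factor effect. The effects are assumed; the protocol gives none.

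| Factor effect | Shift at 20 points | Share of 8.9 min |
|---|---|---|
| 5 min | 1.0 min | 11% |
| 10 min | 2.0 min | 22% |
| 15 min | 3.0 min | 34% |

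If the gap arises by chance, this shift averages to zero over randomisations. If it arises because operators are chosen by arm, it does not. Gaps of 20, 50 and 100 points at 10 min would then give a systematic 2, 5 and 10 min.

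**Average behaviour of the unstratified, unadjusted test.** Simulation with 8,000 runs, 56 evaluable patients, blocks of 4, total SD held at 11.56 and the factor present in half: type I error was about 5% and power about 81% for every factor effect tried.

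**Gain from adjustment.** The residual SD is 11.56 × √(1 − R²), and the noncentrality at 28 per arm is 8.9 / (SD × √(2/28)).

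| R² (assumed) | SD | Noncentrality | Power |
|---|---|---|---|
| 0 | 11.56 | 2.88 | 81% |
| 0.10 | 10.97 | 3.04 | 85% |
| 0.20 | 10.34 | 3.22 | 89% |
| 0.40 | 8.95 | 3.72 | 95% |

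**What stratification adds.** In the same simulation, a factor worth 5, 10 or 15 min has R² = effect² × 0.25 / 11.56², which is 0.05, 0.19 or 0.42. Adjustment alone gave power of 82%, 87% and 96%; stratification plus adjustment gave 83%, 88% and 96%. Stratifying without adjusting made the test conservative, with type I error of 3.0% at 10 min and 1.1% at 15 min.

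**The case against.** Permuted blocks without strata are a legitimate choice in a single-centre trial, and nothing in 6.5.1 is wrong in itself. The SD in 8.4 is a total SD, so 62 patients already pay for the variance from operators and anatomy. Nearly all the power gain comes from covariates, which may be specified in an analysis plan that is not shown, so their absence from the protocol is no finding. Two operators, equal use, the size of their difference and the R² values are all assumed, as is any time gradient with stricture complexity. All of this stands.

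A reader might go further and infer that chance imbalance in 62 patients can by itself mask or mimic the effect. The figures do not support that. A 2 min shift compares with a standard error of 11.56 × √(2/28) = 3.1 min, and significance needs about 6.2 min. At 10 min per operator, imbalance alone would have to reach about 62 points, nearly 5 SDs. Given an unlucky allocation, the operating characteristics are worse: at 10 min, a gap of at least 20 points in either direction raises the false-positive rate to 13%, and one against EndoAngel cuts power to 55%. But those cases are already included in the overall 5% and 81%.

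A reader might also infer that operators will follow the allocation. No passage says so. The protocol only leaves it possible.

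The objection does not reach the recording of operator and stricture class before allocation. That belongs to the randomisation procedure, and an analysis plan cannot restore it afterwards.

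**Conclusion.** The point holds as a design improvement, not as an error in the scheme. Type I error is sound on average. What is left open is (a) a route to bias, if the operator can be chosen with the arm known, whose size depends on operator differences that the protocol does not give; and (b) an avoidable loss of precision, worth about 4, 8 or 14 points of power at 28 per arm if operator and stricture class together explain 10%, 20% or 40% of the variance. The operator part of both presumes more than one endoscopist, which the protocol neither states nor rules out. The stricture part presumes that the MRCP is read before allocation. The Introduction and the eligibility criteria make that feasible, although the table in 1.1 does not list the MRCP. The change is worth making because it is cheap and can only be made before allocation.

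**What to change.** In Protocol 6.5.1, require the operator's identity and the stricture class read from the MRCP to be entered in the electronic system before the randomisation call, and state that the operator is not changed because of the arm. Compare procedure time between arms with adjustment for operator and stricture class.

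State how many endoscopists operate. If there is only one, say so and drop the operator part. If there are several, stratifying by operator is optional: keep the strata few and always pair stratification with adjustment.

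The cost is two extra fields before randomisation and one covariate line. If the list is stratified, the system must also be configured for it, and incomplete blocks may leave the arms slightly unequal.
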